#### **8.4 MODALITIES OF RECRUITMENT**

##### **Selection of sites**

Study site selection will be performed independently in Germany, Austria and Switzerland.

This study will be conducted among sample representatives who are advCSCC-treating physicians (e.g., Dermatology Oncologists, Oncologists, Surgeons). Physicians will be recruited from country-specific physician databases and ADOReg (ADO, Arbeitsgemeinschaft Dermatologische Onkologie; Reg, Registry).

##### **Selection of patients**

In the prospective cohort CSCC patients treated with Cemiplimab and the retrospective cohort patients first diagnosed with advCSCC Jan/2012-Aug/2019 will be selected. These physicians or their assigned staff will be responsible for patient chart identification, qualification and selection, data abstraction, completion of the patient eCRF, resolution of data queries and data validations.

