
RECRUITMENT MODALITIES
	
Selection of Physicians/sites
 
Study site selection will be performed independently in Germany, Austria and Switzerland.
 
This study will be conducted among sample representatives who are advCSCC-treating physicians (e.g., Dermatology- Oncologists, Oncologists, Surgeons). Physicians will be recruited from country-specific physician databases and ADOReg (ADO, Arbeitsgemeinschaft Dermatologische Onkologie; Reg, Registry).
 
Selection of patients
 
These physicians or their assigned staff will be responsible for patient chart identification, qualification and selection, data abstraction, completion of the patient eCRF, resolution of data queries and data validations.

STUDY TREATMENT
	
No investigational agents due to the non-interventional character of the study.
 
Patients may receive any therapies as deemed necessary by their treating physicians for the treatment of advCSCC or other comorbid conditions.

ENDPOINTS / OUTCOMES
	
Data will be summarized descriptively with consideration for the following outcomes of interest:
 
Primary Endpoint: Effectiveness
 
 
○ The primary endpoint is TTNT excluding best supportive care (BSC)
 
 
Secondary Endpoints: Health related outcomes and safety
 
 
○ Secondary endpoints include health related outcomes such as ORR, DOR, DCR, QoL, OS, PFS, pain and safety data.
 

MAIN DATA COLLECTED
	
Prospective cohort:
 
Each patient will be initially treated with Cemiplimab and documented during a follow up time of 36 months according to the usual follow-up in the routine practice.
 
Documentation will be performed up to 8 times:
 
 
• D1: Baseline
 
• D2: after approx. 3 months
 
• D3: after approx. 6 months
 
• D4: after approx. 9 months
 

- D5: after approx. 12 months
- D6: after approx. 18 months
- D7: after approx. 24 months
- D8: after approx. 36 months / end of the Study

In case of Cemiplimab treatment discontinuation in the eCRF at any time, the documentation will continue until D8 or patient's death to assess outcome and further therapeutic modalities, unless the patient withdraws the consent.

The collected data will include:

- Patient and Tumor Characteristics:

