About 16,881 new cases in men and 14,855 cases in women of CSCC were estimated in Germany 2013 (40 / 100,000 people per year resulting in 32,000 CSCC patients annually) (Leiter U, 2014). A high incidence rate is also found in Switzerland (28.9 / 100,000 person per year) (Hollestein LM, 2012; Xiang F, 2014). Although overall CSCC incidence is common, only a small percentage of approx. 5% is expected to progress to mCSCC or ladvCSCC. The majority of CSCC patients can be managed with local therapies (Lippman SM, 1992). The remaining 5% of patients are at high-risk for locally advanced disease and metastasized CSCC. The estimated five-year rate of CSCC recurrence is 8% (Stratigos A, 2015; Levine DE, 2015; Thompson AK, 2016). Larger primary lesions (> 2 cm in diameter), higher histologic grade, particularly thicker lesions, and immune suppressed individuals are considered to be at higher risk for metastasis, with occurrence estimated between 2–5% of patients (Stratigos A, 2015; Thompson AK, 2016). The CSCC lethality rate is difficult to estimate in part due to inaccurate incidence estimates. In Australia the estimated mortality rate is approximately 5%, whereas U.S. studies suggest a rate of 1% (Joseph MG, 1992; Clayman GL, 2005). No standard treatment regimen for advCSCC (mCSCC or ladvCSCC) has been established and tumors are often managed similarly to head and neck SCC. Therefore, patients with advanced disease have a poor survival prognosis. In general, the approach to management relies on surgically removing “satellite or in-transit” metastases around the primary tumor if complete removal is possible. In those with unresectable CSCC, treatment is difficult. A partial response was shown in 44% and a SD in 24% of patients with previously available therapies (Jarkowski et al. 2016). The evidence for effectiveness of currently available systemic therapies for advCSCC is limited to case studies and phase 2 studies with low patient numbers. Generally, advCSCC is chemo responsive; but responses are usually very short-lived and connected to high toxicity, especially in the predominantly elderly patient population.

Radiation therapy alone or in combination with chemotherapy may be used as an alternative option when surgery is not feasible (Stratigos A, 2015). With limited survival, advCSCC (mCSCC and ladvCSCC) have a high unmet medical need (Karia PS, 2013).

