#### **Prospective cohort:**

Each patient will be initially treated with Cemiplimab and documented during a follow up time of 36 months. Documentation will be performed up to 8 times (D1: Baseline, D2: after approx. 3 months, D3: after approx. 6 months, D4: after approx. 9 months, D5: after approx. 12 months, D6: after approx. 18 months, D7: after approx. 24 months, D8: after approx. 36 months / End of the Study). In case of Cemiplimab treatment discontinuation at any time, the documentation will continue until D8 or patient's death to assess outcome and further therapeutic modalities.

The prospective cohort of this observational study plans to collect patients with mCSCC – defined as patients with local/regional (nodal metastasis, field cancerization ect.) as well as distant metastasis (also distant lymph-node), and advCSCC – defined as patients that could not be cured either by curative surgery, curative radiotherapy or both based on a decision of an interdisciplinary tumor board. These patients will receive treatment with Cemiplimab within their clinical routine treatment.

At each participating study site, all advCSCC patients who will initiate treatment with Cemiplimab in a real-world setting will be eligible to participate in the study until the enrollment goal is achieved. The decision to prescribe Cemiplimab will be based solely on the treating physician's clinical judgment. Patients who meet inclusion criteria according to SmPC of Cemiplimab and have signed the ICF will be included in the study.

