#### **Retrospective cohort:**

Patients first diagnosed with advCSCC between Jan/2012 and Aug/2019 will be included and documented at study entry with anonymous data.

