### 8.1 SAMPLE SIZE

Considering the fact that this is a descriptive study, there must be no testing of an *a priori* hypothesis. In our study the primary objective is to describe TTNT or death in 200 patients with advCSCC initially treated with Cemiplimab (prospective cohort) or 200 patients with other therapeutic approaches (retrospective cohort). Sample size justification is described in detail in our synopsis section "STATISTICAL METHODOLOGY."

Approximately 60 participating expert centers located in Germany, and 5 centers from each Austria and Switzerland respectively will participate in the study. Participating centers will include different professional groups with permission for systemic treatment either in university clinics or an office-based setting to get a representative picture of the real-world advCSCC treatment.

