## 11 DATA COLLECTION

### 11.1 DATA COLLECTION

The physicians and/or their assigned staff will be responsible for patient identification, qualification and selection, data abstraction and completion of the patient eCRF. Clinical data will be sourced from patient medical records. Patient data will be de-identified and will be reported in aggregate. eCRFs will be programmed to be available online via encrypted, password protected access. The data entry will be checked for consistency and accuracy.

Following a patient's ICF and enrollment in the study, the frequency with which the patient visits his/her primary CSCC provider will be determined by the local SoC.

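### Section 8.4 leaves the choice of retrospective charts to staff who can see the outcome, with no sampling order and no count of eligible charts, so the historical estimates can be biased in an unknown direction

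*Protocol*

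**What the plan says.** Section 8.4 (Selection of patients) states that the physicians or their staff "will be responsible for patient chart identification, qualification and selection, data abstraction, completion of the patient eCRF". The synopsis repeats this under recruitment modalities: "These physicians or their assigned staff will be responsible for patient chart identification, qualification and selection". Section 11.1 says the same of patients rather than charts: they "will be responsible for patient identification, qualification and selection, data abstraction and completion of the patient eCRF".

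For the retrospective cohort, section 7.1 states: "Patients first diagnosed with advCSCC between Jan/2012 and Aug/2019 will be included and documented at study entry with anonymous data". Sections 7.2, 8.2 and 8.3 add an age limit, the exclusions and the condition that cemiplimab was not planned. Deceased patients may be included. The target is 200 charts from about 70 sites. No section sets a consecutive, random or take-all rule for these charts, a maximum per site, or a log of eligible charts. Site quality control in section 12.2 covers 5% of sites and does not mention which charts were chosen.

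For the prospective cohort, section 7.1 says that at each site "all advCSCC patients who will initiate treatment with Cemiplimab in a real-world setting will be eligible to participate", until the enrolment goal is reached.

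**The concern.** A retrospective chart is opened when its course is already known: time to next therapy, response, progression and often death. If the person who chooses charts sees that, and no rule says which chart comes next, the chance of entering the sample can depend on the outcome. Well-documented courses, long survivors, or striking failures could each be favoured.

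What is at stake is the whole historical half of the study. Retrospective TTNT is part of the primary objective and is reported by Kaplan-Meier for each cohort (section 14.3.2.1). Retrospective PFS and survival proportions (14.3.1.3) and ORR (14.3.2.2) come from the same charts. Section 5.2 intends data from before and after approval to support an assessment of outcomes. The planned confidence intervals measure random error only and would not show this kind of error. A later analysis plan cannot supply the number of eligible charts if sites never recorded it.

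**Working it through.** **1. The plan's own precision figure.** Inputs from the synopsis: 200 patients, 10% censoring, so d = 180 events, and a median of 30 months. For exponential times the 95% limits are 2d × median / χ²(0.975; 2d) and 2d × median / χ²(0.025; 2d). With 2d = 360 this gives 26.06 and 34.91, a width of 8.86. The protocol states 26.1, 34.9 and 8.9, so the table is reproduced. It assumes that the 200 are a random sample.

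**2. Room for choice.**
- Charts per site: 200 / 70 = 2.9 on average. The protocol sets no site quota, so this is not a figure for any one site.
- Window: Jan/2012 to Aug/2019 is 92 months, or 7.67 years.
- National pool: section 5.1 gives German incidence "resulting in 32,000 CSCC patients annually" and about 5% becoming advanced. 32,000 × 0.05 × 7.67 = about 12,270 cases, and 200 / 12,270 = 1.6%. If the advanced share were 2% (assumption), the pool would be about 4,910 and the share 4.1%.
- This pool counts cases that participating sites never saw and charts that the exclusions remove, so 1.6% is a lower-end figure. A second yardstick is the earlier German-Austrian study described in the synopsis, with 190 patients diagnosed over 24 months. Scaled to the window: 190 × 92 / 24 = about 728, and 200 / 728 = about 27%. The protocol does not give that study's completeness or site count, so this too is an assumption.

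Anywhere from 1.6% to 27%, most eligible charts would go undocumented.

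**3. Effect on the median (illustration; the selection ratios are assumptions).** True times are exponential with median 30. Charts with TTNT beyond 30 months are chosen w times as often as the others. The total weight is 0.5 + 0.5w, and the selected median is where half of it, (1 + w)/4, is reached.
- For w > 1, solve w × S(t) = (1 + w)/4. At w = 1.5, S = 0.625 / 1.5 = 0.4167 and t = 30 × log2(1 / 0.4167) = 37.9 months.
- For w < 1, solve 1 − S(t) = (1 + w)/4. At w = 0.67, S = 1 − 0.4175 = 0.5825 and t = 30 × log2(1 / 0.5825) = 23.4 months.

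| w | 0.5 | 0.67 | 0.8 | 1.0 | 1.25 | 1.5 | 2.0 |
|---|---|---|---|---|---|---|---|
| Selected median (months) | 20.3 | 23.4 | 25.9 | 30.0 | 34.6 | 37.9 | 42.5 |

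The planned interval is 26.1 to 34.9. The upper limit is crossed where (1 + w)/(4w) = 2^(−34.9/30) = 0.4465, so w = 1.27. The lower limit is crossed where (3 − w)/4 = 2^(−26.1/30) = 0.5471, so w = 0.81.

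**4. Effect on ORR (same caveat).** Take the 44% partial-response figure for earlier therapies in section 5.1 as a stand-in for the true rate. If responders' charts are chosen 1.5 times as often, the observed rate is 0.44 × 1.5 / (0.44 × 1.5 + 0.56) = 54.1%. At 0.67 times it is 34.5%. The 95% half-width at n = 200 is 1.96 × √(0.44 × 0.56 / 200) = 6.9 percentage points, so both shifts (10.1 and 9.5 points) exceed it.

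**The case against.** The sentence in section 8.4 is a list of site tasks and covers both cohorts. It does not tell anyone to choose by outcome. This stands: the fault is an absent sampling rule, and a reader who infers that the protocol prescribes outcome-based selection goes beyond the text.

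Section 7.1 could be read as taking every eligible patient in the window. With a cap of 200 over about 70 sites, and selection named as a site task, that reading does not hold unless a rule is added.

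The prospective wording opens eligibility to all cemiplimab starters but requires neither consecutive enrolment nor a screening log, so it is not a much stricter rule. The difference that remains is timing: prospective patients enter before their outcome is known.

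A reader might also see a contradiction with the aim "to get a representative picture of the real-world advCSCC treatment" in section 8.1. The documents do not support that. The phrase, like the similar wording in the synopsis and section 8.4, concerns the mix of centres and physicians, not the sampling of charts.

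Finally, deceased patients are expressly allowed, which works against a drift towards survivors, and the study is descriptive without a hypothesis test. The first means that no direction can be assumed. The second does not remove the problem, because a descriptive estimate depends directly on how its sample was drawn.

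**Conclusion.** The point holds as a design gap. As written, the protocol allows selection on a visible outcome into a primary-objective estimate and collects nothing that would reveal it. The retrospective TTNT, PFS, survival and ORR can be biased by chart choice; neither the bias nor its direction is shown.

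At the protocol's 30-month planning median, a selection ratio above about 1.27 or below about 0.81 is enough to move the median outside the planned 95% CI. This rests on exponential times, one cut-point at 30 months and assumed ratios. It shows that modest selection can exceed the random error for which the study was sized, not how large the bias will be.

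Three stronger readings should be avoided. One is that long survivors will be over-represented; nothing in the protocol establishes that. Another is that the sample is 1.6% of what sites could document; that figure uses all estimated German cases, and the share at participating sites is higher and unknown. The third is that anonymity makes the problem irreparable; a site can count its own eligible charts without releasing any identity. The change is worth making, and the protocol is the place for it.

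**What to change.** Add to section 8.4 for the retrospective cohort:
- Each site lists all eligible charts, living or deceased, by date of first advCSCC diagnosis within Jan/2012 to Aug/2019.
- The site documents all of them, or follows a random order supplied by the sponsor across the whole window, up to a stated maximum per site.
- The site reports the numbers eligible, documented and skipped, with reasons for skipping.

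Charts should not be taken consecutively from the earliest date. With about three per site, that would fill the cohort with the oldest cases and replace chart choice with a calendar-period bias. Ordering by diagnosis date matches the way the cohort is defined; ordering by start of therapy would not.

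The cost is a short protocol addition, a little site time for each list, and the need to document some charts with thinner data.

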## 9 CASE REPORT FORM (CRF)

Study data obtained in the course of the study will be recorded on electronic CRFs (eCRF) by trained site personnel. eCRF should be completed for each patient documented in the study. Corrections to the eCRF will be entered in the eCRF by the physician or an authorized designee. All changes, including date, time, and person performing corrections, will be available via the audit trail, which is part of the system. For corrections made via data queries, a reason for any alteration must be provided.

### The following data collection forms will be used for the study:

CSCC patient eCRFs will be used to abstract data from patient medical records and will mainly focus on collection of the data on patient and clinical characteristics, treatment patterns, outcomes, and healthcare resource use, and will cover the period from before mCSCC or advCSCC diagnosis to most recent follow-up or death, whichever comes later.

### PARAMETER AND DEFINITIONS for the CRF's

Outcome(s)	Specific parameter	Definition	Record in Visit (month)
Clinical outcomes	Mortality, all cause, advCSCC related, and date of death	Defined as death due to all cause or disease related	-
	OS from diagnosis	Defined as time from 1 st Cemiplimab treatment until death from any cause, censoring for date of most recent follow-up in surviving patients	-
	Progression	Defined as documented in medical records	3,6,9,12,18,24,36
	Date of progression	Defined as date of first documented progression in the medical record	3,6,9,12,18,24,36
	Time to next treatment (TTNT)	Defined as time from start of Cemiplimab treatment to the start of next systemic therapy or death	-
	PFS	Defined as documented start of systemic Cemiplimab therapy until disease progression or death	3,6,9,12,18,24,36
	Patient		male / female

characteristics	Gender		
	Nationality		Baseline
	Year of birth		Baseline
	Skin phototype	Defined as Type 1, 2.....6	Baseline
	Informed consent		Baseline
	Comorbidities	Auto-immune-disease, hematologic disease, severe cognitive impairment, etc.	Baseline and 3,6,9,12,18,24,and 36
	Quality of life data (QoL)	Questionnaire: EORTC – QoL Core 30	Baseline and 3,6,9,12,18,24,and 36
	Pain	Questionnaire: EORTC – QoL Core 30	Baseline and 3,6,9,12,18,24,and 36
	Adverse events (AE) Quality of life data Reasons for discontinuing therapy Frequency of administration	Defined event as yes/no (specify, related/unrelated to anticancer therapy, serious/non-serious as documented in medical records NOTE: We will limit data collection to Common Terminology Criteria for AE (CTCAE)5.0 as documented in the medical record.Questionnaire: EORTC – QoL Core 30  Defined as lack of response, disease progression, toxicities, side effects, therapy completion, patient decision, death, other (specify) Defined as every day (QD), twice a day (BID), every week (QW), every other week (Q2W), every three weeks (Q3W), every four weeks (Q4W), other	Baseline and 3,6,9,12,18,24,and 36
	Adverse events (AE)	Defined event as yes/no (specify, related/unrelated to anticancer therapy, serious/non-serious as documented in medical records NOTE: We will limit data collection to Common Terminology Criteria for AE (CTCAE) 5.0 as documented in the medical record.	Baseline and 3,6,9,12,18, 24,36
Lab results	Lab parameter LDH		Baseline
Status	Date of physical check-up		Status at Baseline

	Organ transplantation		
	Immunosuppressive therapy		
	Substantial tumor syndromes		
	Specification of substantial tumor syndromes		
	Disease & medication		
Primary diagnosis	Date of diagnosis		All primary diagnosis at Baseline
	Evaluation		
	Tumor status		
	Histological subtype		
	Tumor localization		
	TNM classification		
	Clinical stage		
	ECOG performance status	Defined as 0, 1, 2, 3, 4, measured at advanced diagnosis, at each LOT, prior to and following radiation for early disease, where applicable	
	Infiltration depth and bone involvement		
	Initial treatment of primary tumor		
	Primary surgery	If yes: date, procedure	
	Re-excision	If yes: date, procedure, micrographic controlled surgery, final resection border, cumulative safety distance (cm)	
	Tumor size of the histo block	horizontal tumor diameter (cm), vertical tumor size (mm), differentiation level	
	High risk factors		
	Further synchronous CSCC		
	Curative surgery of advCSCC	Yes or no	
	Tumor board	Yes or no. If yes: decision realized (yes or no)	
	Metastases	Locoal regional or distant	
Recurrence	Date of diagnosis		All recurrence

diagnosis			diagnosis at Baseline
	Evaluation		
	Tumor status		
	Histological subtype		
	Tumor localization		
	TNM classification		
	Clinical stage		
	ECOG performance status	Defined as 0, 1, 2, 3, 4, measured at advanced diagnosis, at each LOT, prior to and following radiation for early disease, where applicable	
	Infiltration depth and bone involvement by local recurrence		
	Initial treatment of primary tumor		
	Primary surgery	If yes: date, procedure	
	Re-excision	If yes: date, procedure, micrographic controlled surgery, final resection border, cumulative safety distance (cm)	
	Tumor size of the histo block	horizontal tumor diameter (cm), vertical tumor size (mm), differentiation level only by local recurrence	
	High risk factors by local recurrence		
	Further synchronous CSCC by local recurrence		
	Curative surgery of ladvCSCC	Yes or no	
	Tumor board	Yes or no. If yes: decision realized (yes or no)	
	Metastases	Locoal regional or distant	
Restaging	Date of diagnosis		All restaging parameters at Baseline
	Evaluation		
	Tumor status		
	Histological subtype		
	Tumor localization		

	TNM classification		
	Clinical stage		
	ECOG performance status	Defined as 0, 1, 2, 3, 4, measured at advanced diagnosis, at each LOT, prior to and following radiation for early disease, where applicable	
	Infiltration depth and bone involvement		
	Differentiation level		
	High risk factors		
	Further synchronous CSCC		
	Response	Yes or no	
	Tumor board	Yes or no. If yes: decision realized (yes or no)	
	Metastases	Locoal regional (type, single or multiple) or distant (localization, single or multiple)	
Surgery	Date of surgery		All at Baseline
	Evaluation		
	Marked lymph nodes (sentinel)	Yes or no	
	Surgery procedure		
	Diameter of largest lymph node	(cm)	
	Capsule break	Yes or no	
	Number of removed lymph nodes		
	Number of lymph nodes with metastases	Maximal size (cm)	
	Completing lymph node dissection	Yes or no If yes: date, procedure, number of dissected lymph nodes, number of lymph nodes with metastases,	
	Residual status		
	Global status of the patient	Tumor free (yes or no)	
Systemic therapy	Intention		All at Baseline
	Line	(1st-line, 2nd-line, ...)	

	Regimen		
	Type	(table with medicinal products, table with study medicinal products, table with toxicity)	
	Therapy	From (date) to (date) or ongoing, number of cycles, application,	
	Best response		
	Reason for therapy completion		
	Table with medicinal products	From (date) to (date) or ongoing. Active ingredient / brand name	
	Table with study medicinal products	From (date) to (date) or ongoing. Type, study, study trial	
	Table with toxicity	Date, event term, severity, medical procedure, outcome.	
Locoregional therapy	Date	From (date) to (date)	All locoregional therapy at Baseline
	Medical examination		
	Intention		
	Therapy procedure		
	Residual status	Locoregional efficacy	
	Global status of the patient	Tumor free or do metastases exist at other location?	
Radio Therapy	Date	From (date) to (date)	All radio therapy at Baseline
	Medical examination		
	Intention		
	Organ system		
	Laterality		
	Type		
	Dosage	(Gray)	
	Residual status	Response rate (no, partial, complete)	
	Global status of the patient	do metastases exist at other location?	
Final patient treatment	Date of last visit		Last and final visit at end of follow-up after 36 months

	Reason of last visit		
	Tumor death relation		
	Date of death		

The following table demonstrate a time table for the e-CRF parameter

	Baseline	Start of Treatment	Visits: Month after start of treatment						
			3	6	9	12	18	24	36
Informed consent	x								
Patient characteristics: Gender, age, skin type etc.	x								
Medical History									
- General medical history (comorbidities, etc.)	x		x	x	x	x	x	x	x
- Any prior autoimmune diseases	x								
- Tumor related history (primary diagnosis, relapses, treatments, etc.)	x		x	x	x	x	x	x	x
Current TNM, Grading (at baseline) and R- Situation if indicated	x		x	x	x	x	x	x	x
QoL (EORTC- QoL Core	x		x	x	x	x	x	x	x

30)									
Adverse Events			x	x	x	x	x	x	x

